3.0 Procedures Involved

3.1 Study Design

Phase 1: *Delivery of educational SSE program.*

Each of the eight changing rooms of the Lynn Sage Comprehensive Breast of Northwestern Memorial Hospital will be equipped with a poster, brochures (Fig 1 and Fig 2) and cards with information about obtaining an appointment with a dermatologist for concerning skin lesions.

A woman research assistant will obtain consent to participate in the research and review of medical information, collect contact information and if the woman owns an iPhone X, 8+ or 8, and ensure receipt of an informational brochure. Women will be asked if they own an iPhone X, 8+ or 8 to assess the prevalence of these specific phones in the population of interest. These iPhones models are of particular interest to the research team as they offer superior image quality compared to older models. If a woman has this type of phone, she will be asked about her experience using it to take close-up pictures. The woman will be asked her preference for being contacted by email, telephone, or text message. The two arms of the study will be delivered on different weeks. During weeks 1,3,5 and 7 of the study period 400 women will be given brochures and a card with information on scheduling dermatology follow-up prior to check-out (Group 1), (Fig 3). During weeks 2, 4, 6 and 8 of the study period, 400 women will be given brochures to perform SSE at home and proceed to check-out of the mammogram area (Group 2). The women in Group 1 will also receive a reminder about performing a SSE one week after their mammogram visit via phone call,

Effect of SSE education delivered during the mammography experience.

email or text message. One month after the mammogram visit both groups will be called and surveyed to see if they checked their skin and/or made an appointment to see a dermatologist. Three months after the mammogram, both groups will be asked to participate in a complete survey (either via REDCap or telephone), including whether the women followed up in dermatology and if any concerning lesions were biopsied.

Fig 1. SSE Poster

[figure not shown]
[figure not shown]

Fig 2. Cover of SSE

[figure not shown]

Phase 2: Assessment of SEE Implementation

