A research assistant will be present at the mammography center to collect consent, telephone numbers, iPhone model information, and email addresses to have women sign onto REDCap to complete a survey. A telephone survey will be administered to each woman enrolled in the study in both groups (N=800) one month after the mammogram asking if she performed a SSE at home and whether a follow-up with dermatology was made. An anonymous REDCap survey may be used in place of the telephone call, depending on participant's preferred method of contact preference. Then, three months after the screening mammogram, an anonymous <2 minute REDCap survey will be sent via email to each woman enrolled in both groups to ascertain the number of women who identified that they were at increased risk for melanoma (history of sunburn, history of indoor tanning >10+sessions, family or personal history of skin cancer), performed a SSE at home, found a concerning lesion, made a follow-up appointment with a dermatologist, and had any concerning lesions biopsied. If participants do not complete the REDCap survey in 2 weeks, they will be called and surveyed via telephone. We anticipate a 20% attrition rate (Fig 3). Participants will be offered a \$10 Amazon gift card in appreciation of completing the one month survey and an additional \$10 for completing of a second REDCap survey three months after the mammogram visit.

Effect of SSE education delivered during the mammography experience.

Fig 3. CONSORT diagram for two arms of study

Effect of SSE education delivered during the mammography experience.

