3.3 Research procedures and activities

Follow-Up

1 week after the mammogram, RA will contact participants in group 1 via their preferred method to remind them to perform SSE and schedule a dermatologist appointment if they find a concerning mole. (see attached telephone script)

1 month after the mammogram, the RA will call participants in group 1 and administer a survey to see if they checked their skin and/or made an appointment with a dermatologist.

Effect of SSE education delivered during the mammography experience.

(see attached telephone script) An anonymous REDCap survey may be used in place of the telephone call, depending on participant's preferred method of contact preference.

The survey questions are as follows:

1. Did you read the brochure?
 Yes No
2. Did you check your skin? (If no, please proceed to question #4)
 Yes No
3. If yes, did you notice any concerning moles?
 Yes No
4. If no, will you consider checking your skin in the future?
 Yes No
5. If you found any concerning moles, did you make an appointment to see a dermatologist?
 Yes No

If no, do you intend to do so in the near future?

6. Did you share the brochure with anyone else?
 Yes No
7. If yes, who did you share it with:
 - a) A relative: son, daughter, father, mother, sister, brother
 - b) A friend : woman, man
 - c) Someone I work with: woman, man

REDCap Survey

3 months after the mammogram, an anonymous REDCap survey will be emailed to each woman enrolled in both groups. If participants do not complete the REDCap survey in 2 weeks, they will be called and surveyed via telephone. The following items with relevance to the research:

1. Do you have a history of sunburn? Yes/No
2. Do you have a history of more than 10 indoor tanning sessions? Yes/No
3. Do you have a personal or family history of melanoma? Yes/No
4. Have you ever performed a skin self-examination prior to your most recent mammogram? Yes/No

Effect of SSE education delivered during the mammography experience.

5. Did you perform a skin self-examination after your most recent mammogram?
Yes/No
If no, then go to item 8.
6. Did you find a concerning mole? Yes/No
7. If you found a concerning mole, did you make an appointment to see a dermatologist? Yes/No
8. If you did not perform a skin self-examination, did you still make a follow-up appointment to see a dermatologist for a skin examination? Yes/No
9. Have you had an appointment with a dermatologist yet? Yes/No

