14.0 Data Analysis

14.1. This convenience sample of women undergoing screening mammography will all receive education either as a brochure and a 1-week reminder or as only the brochure. Demographic characteristics of the two groups will be examined using means and standard deviations (age) and counts and percentages for all categorical variables. Primary outcomes of SSE performance, biopsy, and diagnoses will be compared using Chi-square tests of association or Fisher's exact tests where sample sizes were restrictive. Due to the skewed nature of the anxiety scale, a Wilcoxon rank sum test will be used to compare anxiety, the secondary outcome, in the two groups. Descriptive statistics will be performed for the tertiary outcome of dissemination.

15.0 Confidentiality and Data Management:

1. There are no biological specimens. All of the following data is collected in person consent and responses to structured interviews and focus groups.
2. Our systems are guarded against outside entry by Northwestern's own firewall supporting 128-bit encryption. This level of encryption provides the highest level of protection against hackers, computer break-ins, etc. All data is deidentified. Experienced research assistants will be employed and will receive training that includes emphasis upon the importance of confidentiality of information, and all personnel on the project will complete the required NIH training in the protection of human research participants.
3. Data will be retained in separate locked file cabinets and on computers with restricted and password protected access, without links to the master code list. All data based on the research will be reported in aggregate form. No individual respondents will be identified. Electronic data will be maintained in a study specific database on the server of the Department of Dermatology at the Feinberg School of Medicine. Paper-based files will be kept in a locked cabinet in a locked room within the Northwestern University Department of Dermatology research offices. Identifiable data will be kept separate from the case report forms and source documents. Data gathered as a result of this study are available to inspection on request by Food and Drug Administration or other government regulatory agency auditors, and the Northwestern University Institutional Review Board (IRB).

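### Sections 3.1 and 3.3 disagree on who gets the 1-month survey, and the undated 3-month item cannot separate skin self-examination done before that survey from that done after it

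*Combined protocol and SAP*

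**What the plan says.** **Who gets the 1-month survey.** Section 3.1 Study Design, Phase 1, gives it to both arms: "One month after the mammogram visit both groups will be called and surveyed to see if they checked their skin". Phase 2 of the same section repeats this with the full sample: "A telephone survey will be administered to each woman enrolled in the study in both groups (N=800) one month after the mammogram". Section 3.3, under Follow-Up, differs: "the RA will call participants in group 1 and administer a survey to see if they checked their skin". It gives no matching instruction for Group 2.

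**What that survey asks.** It asks whether the woman checked her skin, with no reference period. Those who did not are asked "If no, will you consider checking your skin in the future". It contains no instruction to perform SSE.

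**What differs between arms by design.** "The women in Group 1 will also receive a reminder about performing a SSE one week after their mammogram visit via phone call" (or by email or text). Group 1 also receives a card on scheduling a dermatology appointment.

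**What is measured at 3 months.** Item 5 of the 3-month survey asks "Did you perform a skin self-examination after your most recent mammogram", with no date or window beyond that.

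**What is analysed.** Section 14.0: "Primary outcomes of SSE performance, biopsy, and diagnoses will be compared using Chi-square tests of association". Neither 14.0 nor 3.4 Measures says whether the 1-month or the 3-month SSE answer is meant.

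**The concern.** The Group 1 intervention is itself a brief contact about SSE. Three weeks after the reminder, a research contact raises the same behaviour and asks non-performers whether they will consider it. SSE begun after that contact counts at 3 months exactly as SSE begun after the reminder does.

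The consequence depends on which section staff follow. Under 3.3, one arm gets a second contact that the other does not, so the 3-month difference could be inflated even if the Group 1 package does nothing. The 1-month comparison would also be lost, because controls would have no 1-month answer. Under 3.1, both arms get the contact. More control women would still be unexamined at that point if the package works, so later uptake could narrow the gap. The two paths push the 3-month result in opposite directions.

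**Working it through.** **Plan's own figure.** The sample size is N=800, 400 per group. It cannot be reproduced, because the documents give no alpha, power, SSE rates or effect size.

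**Inputs from the documents.** 400 per group (3.1, Phase 1) and 20% anticipated attrition (3.1, Phase 2), so 400 × 0.8 = 320 evaluable per arm.

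**Assumptions, none in the documents.** Two-sided alpha of 0.05; SSE rates p1 (Group 1) and p2 (Group 2) before the 1-month contact; and q, the share of women not yet examined who do SSE after that contact. Women are treated as independent, every evaluable woman receives the contact where her arm is due it, and there is no other uptake in months 2-3.

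**Formulas.**
- 3-month rate in a contacted arm = p + (1 − p)q.
- Power = Φ[(d − 1.96 × SE0)/SE1], where d is the absolute difference, SE0 = √[2 × p̄(1 − p̄)/n], SE1 = √{[p1(1 − p1) + p2(1 − p2)]/n}, p̄ is the mean of the two rates and n = 320.

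**Path A: only Group 1 surveyed (3.3), no package effect, 40% v 40%.**
- q = 0.1: Group 1 = 0.40 + 0.60 × 0.1 = 46%. Spurious difference 6 points; probability of significance 0.33.
- q = 0.2: Group 1 = 0.40 + 0.60 × 0.2 = 52%. Spurious difference 12 points; SE0 = 0.0394, SE1 = 0.0391, (0.12 − 0.0772)/0.0391 = 1.09; probability 0.86.

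**Path B: both groups surveyed (3.1), same q in each arm.** The 3-month difference is (1 − q) times the 1-month difference.

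| Rates before survey (Group 2 v Group 1) | q | 3-month rates | Difference | Power |
|---|---|---|---|---|
| 30% v 40% | 0 | 30 v 40 | 10 points | 0.76 |
| 30% v 40% | 0.1 | 37 v 46 | 9 points | 0.64 |
| 30% v 40% | 0.2 | 44 v 52 | 8 points | 0.53 |
| 40% v 50% | 0 | 40 v 50 | 10 points | 0.72 |
| 40% v 50% | 0.2 | 52 v 60 | 8 points | 0.53 |
| 60% v 70% | 0 | 60 v 70 | 10 points | 0.76 |
| 60% v 70% | 0.2 | 68 v 76 | 8 points | 0.62 |

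With p1 = p2 and equal q, the expected 3-month difference is zero, so path B produces no false positive.

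**Direction under path B if responses differ.** The gap narrows only if q2(1 − p2) > q1(1 − p1). At 50% v 40% that means q1/q2 < 0.6/0.5 = 1.2. With q1 = 0.1 and q2 = 0.2 the rates are 55% v 52%, a 3-point gap. With q1 = 0.2 and q2 = 0.1 they are 60% v 46%, a 14-point gap.

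**The case against.** A reader might infer that the 1-month survey acts as a late reminder to every woman, that the reminder's effect is therefore diluted, and that the 3-month comparison is invalid whichever section is followed. The documents do not support that.

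- The survey asks about SSE but does not tell anyone to do it, unlike the 1-week contact. Nothing in the documents sizes its effect. Section 3.2 lists the same question about future checking in a survey described at enrolment; if it is given then, both arms meet the cue before the 1-month contact.
- No SSE time point is named, so harm from path B arises only if the 3-month answer is the one tested. The 1-month answer is taken before the survey can act.
- With identical contact in both arms, the 3-month comparison still validly compares the arms under the study's own follow-up. The contrast is also the whole Group 1 package, card included, and not the reminder alone.
- The direction depends on how each arm responds, and every rate and q is assumed. The model credits all later uptake to the survey and ignores 1-month non-response, so it probably overstates the loss for a given amount of late uptake.
- Section 3.3's restriction to Group 1 may be a drafting slip. Section 3.1 says both groups twice, and 12.0 pays for the 1-month survey with no limit by arm.

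These objections stand, and they reduce dilution to a conditional loss of power. They do not remove the contradiction between 3.1 and 3.3, the undated 3-month item or the unnamed time point.

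**Conclusion.** The point holds in limited form. The firm part is textual: the plan gives two incompatible instructions on who receives the 1-month survey, and the 3-month item cannot show whether SSE came before or after it. Following 3.3 could bias the 3-month result in favour of Group 1 (0 to 6 points spurious at q = 0.1, 0 to 12 at q = 0.2, if 40% of each arm would otherwise perform SSE) and would leave no control answer at 1 month.

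Following 3.1 avoids that bias. What remains is a likely loss of power at 3 months if the arms respond similarly: from 76% to 64% or 53% at 30% v 40%, less at higher rates. A clearly stronger response in Group 1 would widen the gap instead. All of these sizes are illustrations on assumed rates, response shares and alpha. The correction is worth making because it is cheap and the primary SSE time point is still open.

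**What to change.** 1. Correct 3.3 to match 3.1, so that both groups get the identical 1-month survey in the same way.
2. Anchor the 1-month SSE question with *since your mammogram*. Without this it is less well defined than the 3-month item.
3. Add to 3-month item 5: *If yes, was the first time before or after our 1-month survey?* This works within one survey, which matters because the REDCap surveys are described as anonymous and linking a woman's answers across surveys may not be possible.
4. State in 14.1 which SSE time point is primary. The 1-month answer is preferred for the effect of the Group 1 package (1-week reminder plus scheduling card), because it is taken before the survey can act. Report 3-month SSE as secondary, and keep 3 months for dermatology visits and biopsies, which need the time.

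**Cost.** Wording in two sections, one anchoring phrase and one sub-item; no women or contacts beyond those 3.1 already plans. Choosing 1 month is partly a choice of estimand, early response rather than uptake by 3 months, so SSE first done in months 2-3 would not count toward the primary outcome. The timing sub-item relies on recall.

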3.1 Inclusion Criteria for Patient

Women 18 years of age and older, who are waiting to have a mammogram

Women agree to complete informed consent and registration forms allowing follow-up reminders and access to their EMR record limited to the visit with a dermatologist or primary care physician regarding a concerning skin lesion and the results of the biopsy of the lesion.

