10. If you found a concerning mole and saw a dermatologist, was the concerning mole biopsied? Yes/No
 - a. If yes, was the biopsy done at Northwestern? Yes/No
 - b. If No, were you told by your dermatologist that the skin biopsy was melanoma? Yes/No
11. If you saw a dermatologist, were any other concerning moles biopsied? Yes/No

EMR review

If a woman responds yes to item 9 indicating that they made an appointment with a dermatologist, then the EMR will be checked to ascertain the findings of the dermatologist. The pathology report of biopsied mole(s) will be reviewed and added to the deidentified database.

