3.4 Measures

The number of women with risk factors for melanoma, who performed SSE after the screening mammogram, who found a concerning mole, who saw dermatology, who had a concerning lesion biopsied in each group will be analyzed by descriptive statistics. The difference in proportions of women who 1) performed SSE 2) saw a dermatologist in the educational intervention group from the intensive intervention group will be compared using a χ^2 test. If the woman responded “yes” to follow-up in dermatology, a chart review of the electronic medical record will be performed to assess whether any lesions were biopsied and pathology of the concerning lesions. The accuracy of the woman’s selection of a concerning lesion will be assessed by examining the correspondence rate between the woman’s assessment during SSE and the dermatologist. The overall correspondence rate will be calculated with a random intercept-only mixed logistic regression model. The statistical analysis will be performed by [name], MPH.

Online data

REDCap survey (see page 8 above)

Approvals required

Effect of SSE education delivered during the mammography experience.

[name] obtained permission for this research to be conducted in the Lynn Sage Comprehensive Breast Center of Northwestern Medicine/Prentice Women's Hospital

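### Chart review opens only after a survey yes, so the anticipated 20% who stop answering can lose biopsy and diagnosis data that enrolment consent would partly let the study recover

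*Combined protocol and SAP*

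**What the plan says.** **Loss.** Section 3.1 Study Design, Phase 2, states "We anticipate a 20% attrition rate (Fig 3" directly after describing the three-month survey and the telephone call to women who have not completed it within two weeks. The figure is not split by arm and is not tied in words to one survey.

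**Chart trigger.** Section 3.3, EMR review: "If a woman responds yes to item 9 indicating that they made an appointment with a dermatologist, then the EMR will be checked". Item 9 belongs to the three-month survey. Section 3.4 Measures says that after a yes to dermatology follow-up "a chart review of the electronic medical record will be performed to assess whether any lesions were biopsied and pathology of the concerning lesions", but does not say which survey supplies the yes. No section describes a chart check for a woman who does not answer.

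**Consent.** Under section 3.1 Inclusion Criteria, every participant signs forms "allowing follow-up reminders and access to their EMR record". That access is limited to a dermatology or primary care visit about a concerning lesion and to the biopsy result. It does not depend on a survey reply. Section 13.2 describes EMR access only for women who have had a dermatology visit for a concerning mole.

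**Analysis.** Section 14.0 names skin self-examination (SSE), biopsy and diagnoses as primary outcomes, compared by chi-square or Fisher's exact test. It gives no denominator, missing-data rule or sensitivity analysis, and does not say whether the one-month or the three-month SSE answer is analysed.

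**One-month survey.** Section 3.1 says "A telephone survey will be administered to each woman enrolled in the study in both groups (N=800) one month after the mammogram". Section 3.3 describes that call for Group 1 only.

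**The concern.** Biopsy and pathology are events that the site's own records can show without the woman's help. The plan nevertheless places a self-report gate in front of the record. A woman who has a Northwestern biopsy and then ignores the three-month survey contributes nothing, although she agreed at enrolment to that record being read.

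Biopsies and diagnoses are likely to be few, so each lost event counts. Women who ignored the brochure may also be the ones who ignore the survey, in which case loss depends on outcome. Loss may differ by arm too, because only Group 1 has the one-week contact, which could raise engagement or cause fatigue. With no denominator stated, the analyst must choose after the fact between dropping these women and scoring them as no event, and the two choices can push the comparison in opposite directions.

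**Working it through.** **Inputs from the documents.** N = 800; 400 per arm (Group 1: "400 women will be given brochures and a card with information on scheduling dermatology follow-up"; Group 2: "400 women will be given brochures to perform SSE at home"); 20% attrition. No alpha, power, event rate, survey response rate or evaluable number is given in the text, so there is no power figure to reproduce. Every rate used in steps 3 and 4 is an assumption.

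**1. Women affected.** 0.20 × 800 = 160 (80 per arm if loss is equal), leaving 640 (320 per arm). For biopsy and diagnosis this is an upper limit: under the section 3.4 wording, a one-month yes about dermatology might also open a chart.

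**2. Precision.** The standard error is proportional to 1/√n. √(640/800) = 0.894, a fall of about 11%, reached only if the outcome is established for every lost woman. If a share f is recovered, n per arm is 400 × (0.80 + 0.20f): 340, 360, 380 and 400 for f = 25%, 50%, 75% and 100%.

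**3. Worst-case bounds.** Suppose responders show 15% in Group 1 and 10% in Group 2, with 20% missing in each arm.
- Lower bound: 0.8 × 0.15 − (0.8 × 0.10 + 0.2) = −0.16.
- Upper bound: (0.8 × 0.15 + 0.2) − 0.8 × 0.10 = +0.24.

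The width is 2 × 0.20 × (1 − f): 40 points with nothing recovered, then 30, 20, 10 and 0 points for the four values of f above.

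**4. Bias illustrations.** The true rate is the same in both arms, so any difference shown is false (Group 1 minus Group 2, in points).

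| True rate | Loss, G1 v G2 | Lost women's rate | Handling | Shown, G1 v G2 | False difference |
|---|---|---|---|---|---|
| SSE 40% | 15% v 25% | half the responders' | dropped | 0.40/0.925 = 43.2% v 0.40/0.875 = 45.7% | −2.5 |
| SSE 40% | 15% v 25% | zero | dropped | 0.40/0.85 = 47.1% v 0.40/0.75 = 53.3% | −6.3 |
| SSE 40% | 20% v 20% | half the responders' | dropped | 0.40/0.90 = 44.4% in both | 0 |
| Visit 10% | 15% v 25% | half the true rate | dropped | 0.0925/0.85 = 10.9% v 0.0875/0.75 = 11.7% | −0.8 |
| Visit 10% | 20% v 20% | half the true rate in G1, same in G2 | dropped | 0.09/0.80 = 11.25% v 0.08/0.80 = 10.0% | +1.25 |
| Visit 10% | 15% v 25% | same | counted as no event | 0.10 × 0.85 = 8.5% v 0.10 × 0.75 = 7.5% | +1.0 |

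In the first and third rows the divisors are 0.85 + 0.15/2, 0.75 + 0.25/2 and 0.80 + 0.20/2. In the fourth and fifth rows each numerator is the true rate less the lost women's share, for example 0.10 − 0.15 × 0.05 = 0.0925. The sign changes with the pattern of loss and with the handling. Equal loss with equal relative rates gives no false difference. The SSE rows cannot be helped by charts; only the visit rows resemble an outcome that a chart could supply.

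**5. Using the one-month answer.** If only Group 1 is called at one month, carrying a yes forward can raise SSE in Group 1 alone. The substitution is even-handed only if both groups are asked.

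**The case against.** The strongest case on the other side is that the plan already limits loss, and that reading every chart could add bias.

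- **Mitigation exists.** There is a telephone call after two weeks, a choice of contact method, and a $10 card for each of the two follow-up surveys. This stands, but 20% is what the plan still expects with these in place.
- **Consent is narrower than it looks.** A reader might infer that enrolment consent allows open chart follow-up. It does not: it covers concerning-lesion visits and biopsy results. Visits without a lesion, which Aim 2 counts, fall outside it, and section 13.2 is narrower still. Searching all 800 charts means opening records of women with no such visit. The consent form is not in the material at hand, so its wording must be confirmed. This stands.
- **A Northwestern-only outcome may differ by arm.** Outside care is expected: the three-month survey asks where the biopsy was done, and section 10.1 sends concerned control subjects to their own dermatologist. Group 1 is handed a scheduling card. Where it directs women is not stated, and appointment cards are also placed in the changing rooms, but if it steers care to Northwestern, a record-only outcome would under-count Group 2. This stands, and it shapes the fix.
- **The surveys are called anonymous.** This does not defeat the point. Calling individual non-completers and opening a chart after an individual yes both require identified three-month replies, and a chart check needs only enrolment identity. Linkage of a one-month REDCap reply does need confirming.
- **A one-month yes is not a certain three-month yes.** The one-month question has no time anchor, whereas the three-month question refers to the period since the mammogram. No one-month response rate is given either, so how many missing women it would cover is unknown. This stands.

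**Conclusion.** The point holds in a limited form. Followed as written in section 3.3, the plan forgoes recoverable events on two of its three primary outcomes among up to 160 of 800 women, and says nothing about how those women enter the analysis. It should be changed, at modest cost.

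Three stronger readings are tempting and are not supported:

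- **That the tests will certainly run on responders only.** No denominator is stated; counting lost women as no event is equally open, and Fig 3, which might give analysed numbers, is not shown.
- **That all 160 certainly lack data.** Section 3.4 leaves room for a one-month yes to open a chart, and attaching the 20% to the three-month survey is the natural reading of its position, not a stated fact.
- **That the comparison is biased by 2.5 or 6.3 points.** Those figures concern SSE and rest on an assumed 40% rate, an assumed 15% v 25% split and assumed behaviour of lost women. The documents give only 20% overall.

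The direction and size of any bias are therefore unknown. The precision gain from charts is at most 11% of the standard error and will be smaller, since outside care and lesion-free visits remain survey-only.

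**What to change.** 1. **Chart check.** Amend sections 3.3, 3.4 and 13.2 so that, at one fixed time after the mammogram and within the consent's scope, the EMR of every consented woman, including survey non-responders, is checked for a concerning-lesion visit, biopsy and pathology. This also settles which survey reply, if any, opens a chart.
2. **Outcome definition.** Keep the outcome as survey plus EMR combined. Show Northwestern-recorded and outside care separately by arm. Do not treat the absence of a Northwestern record as proof of no event.
3. **Denominator.** State in section 14.0 who is counted in each comparison, and add a sensitivity analysis scoring non-responders as no event. Report survey response by arm.
4. **One-month SSE answer.** Reconcile section 3.3 (Group 1 only) with section 3.1 (both groups). Only if both groups are asked and replies can be linked, use a one-month yes where the three-month answer is missing, as a sensitivity analysis, with missing counted as not performed alongside it.

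**Cost.** Brief look-ups on up to 800 charts instead of only those of women who reported a visit, with no extra patient contact, and confirmation that the consent form covers them. If it does not, the form has to be changed before the check is extended.
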